3.1.3 Safety Follow-Up Period

Participants will return to the site for a Safety Follow-up Visit (Visit 5) approximately 4 weeks after the end of the Treatment Period for safety and PK assessments.

3.1.4 Pharmacokinetic Period

Participants will return to the site for 2 PK Visits (Visits 6 and 7) approximately 8 and 15 weeks, respectively, after the end of the Treatment Period for safety and PK assessments.

3.1.5 Coronavirus Disease 2019 Contingency Measures

In cases of COVID-19 limitations, it is the Investigator's responsibility to assure the safety of participants, including phone or video contact to assess the participant's well-being including any AE, collection of study samples and clinical data as best as possible, and direct shipment of study drug to participant, if necessary. Where available and appropriate, home health care may be considered to facilitate monitoring of safety and study continuity. Documentation of these cases and the site's management of participants should be recorded in the Investigator study files. In the

absence of a COVID-19 impact, it is expected that Investigators and participants follow the protocol requirements as set forth.

3.2 Study Indication

The indication for this study is dyslipidemia.

4 SELECTION AND WITHDRAWAL OF PARTICIPANTS

4.1 Inclusion Criteria

Participants who meet all of the following criteria will be eligible to participate in the study:

- 1. Understanding of the study procedures, willingness to adhere to the study schedules, and agreement to participate in the study by giving written informed consent prior to screening procedures;
- 2. Men or women 18 to 75 years of age, inclusive, at the Screening Visit;
 - o Women may be enrolled if all 3 of the following criteria are met:
 - They are not pregnant;
 - They are not breastfeeding; and
 - They do not plan on becoming pregnant during the study;
 - O Women of childbearing potential must have a negative urine pregnancy test at the Screening Visit. Note: Women are not considered to be of childbearing potential if they meet 1 of the following criteria as documented by the Investigator:
 - They have had a hysterectomy or tubal ligation at a minimum of 1 cycle prior to signing the ICF; or
 - They are postmenopausal, defined as ≥1 year since their last menstrual period for women ≥55 years of age or ≥1 year since their last menstrual period and have a follicle-stimulating hormone (FSH) level in the postmenopausal range for women <55 years of age; and

 - O Women of childbearing potential must agree to use an effective method of avoiding pregnancy from screening to 90 days after the last visit. Men whose partners are of childbearing potential must agree to use an effective method of avoiding pregnancy from screening to 90 days after the last visit. Effective methods of avoiding pregnancy are contraceptive methods with a Pearl index of <1 used consistently and correctly (including implantable contraceptives, injectable contraceptives, oral contraceptives, transdermal contraceptives, intrauterine devices, diaphragm with spermicide, male or female condoms with spermicide, or cervical cap) or a sterile sexual partner;
- 3. Fasting LDL-C levels >70 mg/dL and TG levels <400 mg/dL at the Screening Visit; and
- 4. Currently receiving high-intensity statin therapy (atorvastatin 40 or 80 mg or rosuvastatin 20 or 40 mg) at a stable dose for 8 weeks prior to screening and intending to remain at the same stable dose throughout the study duration.

4.2 Exclusion Criteria

Participants who meet any of the following criteria will be excluded from participation in the study:

- 1. Body mass index \geq 40 kg/m² at the Screening Visit;
- 2. Current clinically significant CV disease, including but not limited to:
 - o Major adverse CV event within 3 months prior to randomization; or
 - New York Heart Association Functional Classification Class III or IV heart failure;
- 3. Glycosylated hemoglobin (HbA1c) ≥10% at the Screening Visit;
- 4. Uncontrolled hypertension, ie, sitting systolic blood pressure >160 mmHg and/or sitting diastolic blood pressure >90 mmHg. One retest will be allowed, at which point if the retest result is no longer exclusionary, the participant may be randomized;
- 5. Active muscle disease or persistent creatine kinase concentration >3 × the upper limit of normal (ULN). One retest will be allowed after 1 week to verify the result, at which point if the retest result is no longer exclusionary, the participant may be randomized;
- 6. Estimated glomerular filtration rate <60 mL/min, calculated using the Chronic Kidney Disease Epidemiology Collaboration equation;⁶
- 7. Hepatic dysfunction as evidenced by any laboratory abnormality as follows: gamma-glutamyl transferase, alanine aminotransferase, or aspartate aminotransferase >2 × ULN, or total bilirubin >1.5 × ULN;
- 8. Anemia, defined as hemoglobin concentration <11 g/dL for men and hemoglobin concentration <9 g/dL for women;
- 9. History of malignancy within 5 years prior to screening, with the exception of non-melanoma skin cancers;
- 10. History of alcohol and/or drug abuse within 5 years prior to screening;
- 11. Treatment with other investigational products or devices within 30 days or 5 half-lives, whichever is longer, prior to screening;
- 12. Treatment with any proprotein convertase subtilisin kexin type 9 (PCSK9) inhibitor within 10 weeks prior to randomization or bempedoic acid within 2 weeks prior to randomization;
- 13. Evidence of any other clinically significant, non-cardiac disease or condition that, in the opinion of the Investigator, would preclude participant in the study; or
- 14. Known CETP inhibitor allergy or intolerance.

4.3 Retesting

If laboratory abnormalities during screening are considered by the Investigator to be transient, then the laboratory tests may be repeated once during screening. The Investigator's rationale for retesting should be documented. If the retest result is no longer exclusionary, the participant may be randomized.

4.4 Rescreening

A participant who is screened and does not meet the study eligibility criteria may be considered for rescreening upon Sponsor and/or Medical Monitor consultation and approval. Rescreened participants will be assigned a new participant number. Rescreening should occur no less than 5 days after the last Screening Visit.

4.5 Withdrawal Criteria

Participation in this study may be discontinued for any of the following reasons:

- The participant withdraws consent or requests discontinuation from the study for any reason;
- Occurrence of any medical condition or circumstance that exposes the participant to substantial risk and/or does not allow the participant to adhere to the requirements of the protocol;
- Any SAE, clinically significant AE, severe laboratory abnormality, intercurrent illness, or other medical condition, which indicates to the Investigator that continued participation is not in the best interest of the participant;
- Pregnancy;
- Requirement of prohibited concomitant medication;
- Participant failure to comply with protocol requirements or study-related procedures; or
- Termination of the study by the Sponsor or the regulatory authority.

Unless the participant withdraws consent, participants who discontinue study drug early should be encouraged to complete the full panel of assessments scheduled for the Early Termination Visit promptly and complete a Safety Follow-up Visit 4 weeks after the last dose. If a participant withdraws prematurely from the study due to the above criteria or any other reason, study staff should make every effort to complete the full panel of assessments scheduled for the Early Termination Visit and complete a Safety Follow-up Visit 4 weeks after the last dose. PK samples will not be collected during the Safety Follow-up Visit for participants who discontinue study drug early without withdrawing consent or for participants who withdraw prematurely from the study. The reason for participant withdrawal must be documented in the electronic case report form (eCRF).

In the case of participant lost to follow-up, attempts to contact the participant must be made and documented in the participant's medical records.

Withdrawn participants will not be replaced.

5 STUDY TREATMENTS

5.1 Treatment Groups

Participants will be randomized in a 1:1:1 ratio to 1 of the following treatment groups:

- 5 mg obicetrapib (one 5 mg obicetrapib tablet + 1 placebo tablet);
- 10 mg obicetrapib (two 5 mg obicetrapib tablets); or
- Placebo (2 placebo tablets).

5.2 Rationale for Dosing

In previous clinical studies of obicetrapib in healthy volunteers and patients, near maximal effects were observed at the 5 mg obicetrapib dose level with increased HDL-C levels and decreased LDL-C levels. A statistically significant reduction in Lp(a) levels from baseline was also observed at the 10 mg obicetrapib dose level. Therefore, the present study will utilize doses of 5 and 10 mg obicetrapib in participants currently receiving high-intensity statin therapy.

5.3 Randomization and Blinding

Participants who meet all eligibility criteria will be randomized into the study. Participants will be randomized in a 1:1:1 ratio to the 5 mg obicetrapib, 10 mg obicetrapib, or placebo treatment groups. At randomization, participants will be stratified according to their Screening Visit (Visit 1) LDL-C level (≥100 or <100 mg/dL). An automated interactive response technology (IRT) system will be used to assign the participant to 1 of the 3 treatment groups.

Participants, Investigators, the CRO, and the Sponsor will be blinded to all lipid results from Day 1 (Visit 2) for the first participant through database lock in order to protect blinding to treatment assignment.

5.4 Breaking the Blind

Unblinding by request of an Investigator should occur only in the event of an emergency or AE, for which it is necessary to know the study drugs to determine an appropriate course of therapy for the participant. If the Investigator or qualified designee must identify the treatment assignment of an individual participant, the Investigator or qualified designee should request the treatment assignment from the IRT system. The Investigator is advised not to reveal the treatment assignment to other sites or Sponsor personnel.

Prior to unblinding, and if the situation allows, the Investigator should consult with the Sponsor's Medical Monitor. If this is impractical, the Investigator must notify the Sponsor's Medical Monitor as soon as possible, without revealing the treatment assignment of the unblinded participant. The Investigator must document the participant identification and the date and time for breaking the blind and must clearly explain the reasons for breaking the blind.

Medically necessary care should not be delayed for unblinding information (ie, the Investigator should treat the participant based on the participant's signs/symptoms without waiting for the unblinding process to be completed).

For participants who are unblinded and withdrawn from the study, study staff should make every effort to complete the full panel of assessments scheduled for the Early Termination Visit and complete a Safety Follow-up Visit 4 weeks after the last dose.

5.5 Drug Supplies

5.5.1 Formulation and Packaging

The study drugs will consist of 5 mg obicetrapib tablets and matching placebo tablets. All study drugs are manufactured in accordance with current Good Manufacturing Practice.

Obicetrapib tablets are round, 6 mm in diameter, white film-coated tablets, with no identifying markings, containing 5 mg of obicetrapib drug substance. Matching placebo tablets will also be provided.

Obicetrapib and placebo tablets will be packaged into foil blisters and assembled into blister cards providing the study drugs for each treatment group. The blister cards will be clearly labelled to indicate which blisters to use on each day. The tablets should be stored at ambient conditions below 25 °C (77 °F).

The physical, chemical, and pharmaceutical formulation properties and characteristics of the obicetrapib tablets are described in the Investigator's Brochure.

All study drugs will be labelled in accordance with all applicable local regulatory requirements.

5.5.2 Study Drug Preparation and Dispensing

The study drugs used in this study are as follows:

- 5 mg obicetrapib tablet; and
- Matching placebo tablet.

The study drugs listed above will be packaged to provide doses of 5 or 10 mg obicetrapib or placebo only. Participants will be randomized to receive 1 of the 2 doses of obicetrapib or placebo only on Day 1 to Day 56.

At each appropriate visit (Visits 2 and 3), participants will receive 4 blister cards with the study drugs appropriate for the participant's treatment group. Each blister card will provide a sufficient supply for 1 week of dosing, with enough for an extra day of dosing in case the participant needs to postpone the next visit. Participants will be instructed to take 2 units from the blister cards each day. The blister cards will be clearly labelled to indicate which blisters to use on each day. Participants will be instructed to bring all unused study drugs to the site at the next visit.

This study protocol includes contingency measures to manage disruptions due to COVID-19 control measures, including modifications to study drug dispensation specific to situations where COVID-19 is impacting study conduct. See Section 3.1.5 for details of COVID-19 contingency measures. In the absence of a COVID-19 impact, it is expected that Investigators and participants follow the protocol requirements as set forth.

5.5.3 Study Drug Administration

Two tablets of study drugs will be administered by the participant orally and once daily on Day 1 to Day 56. Study drugs should be administered at approximately the same time each morning, with food. On days with visits scheduled, study drugs should be administered with food following all fasted blood samples. If a participant forgets to take study drug on a given day, they should take the next dose as normal and should not take a double dose to make up for the forgotten dose.

5.5.4 Treatment Compliance

Compliance to the study drug regimen will be evaluated by counting unused tablets. Participants will be instructed to bring all unused study drugs to the site at Visits 3 and 4. During the Treatment Period, if compliance is not between 80% and 120%, inclusive, the participant will be counselled about the importance of compliance to the regimen. If the limits are exceeded at 2 consecutive visits, a decision will be made by the Investigator and Sponsor as to whether the participant should be withdrawn from the study.

5.5.5 Storage and Accountability

All study drugs must be stored below 25 °C (77 °F) in a secure area with access limited to the Investigator and authorized site personnel.

In accordance with regulatory requirements, the Investigator or designated site personnel must document the amount of study drug dispensed and/or administered to participants, the amount returned by participants, and the amount received from and returned to the Sponsor (or representative) when applicable. Study drug accountability records must be maintained throughout the course of the study. The accountability unit for this study is a tablet. Discrepancies are to be reconciled or resolved. Procedures for final disposition of unused study drug will be provided in the appropriate study manual.

5.6 Prior and Concomitant Medications and/or Procedures

5.6.1 Excluded Medications and/or Procedures

Participants must not receive treatment with other investigational products or devices within 30 days or 5 half-lives, whichever is longer, prior to screening.

Participants must abstain from taking any PCSK9 inhibitor within 10 weeks prior to randomization or bempedoic acid within 2 weeks prior to randomization.

5.6.2 Allowed Medications and/or Procedures

Participants must be currently receiving high-intensity statin therapy (atorvastatin 40 or 80 mg or rosuvastatin 20 or 40 mg) at a stable dose for 8 weeks prior to screening and intending to remain at the same stable dose throughout the study duration.

5.6.3 Documentation of Prior and Concomitant Medication Use

Medications used within 28 days prior to the Screening Visit will be recorded. Any medications administered in addition to the study drugs, whether allowed per the protocol or not, must be documented on the concomitant medication eCRF.

6 STUDY PROCEDURES

Study procedures will follow the Schedule of Procedures (Appendix A).

This study protocol includes contingency measures to manage disruptions due to COVID-19 control measures, including modifications to visit schedules and procedures specific to situations where COVID-19 is impacting study conduct. See Section 3.1.5 for details of COVID-19 contingency measures. In the absence of a COVID-19 impact, it is expected that Investigators and participants follow the protocol requirements as set forth.

7 EFFICACY ASSESSMENTS

The primary efficacy endpoint is the percent change from Day 1 to Day 56 in LDL-C for each obicetrapib group compared to the placebo group.

The key secondary efficacy endpoints include the following:

- Percent change from Day 1 to Day 56 in ApoB for each obicetrapib group compared to the placebo group;
- Percent change from Day 1 to Day 56 in non-HDL-C for each obicetrapib group compared to the placebo group; and
- Percent change from Day 1 to Day 56 in HDL-C for each obicetrapib group compared to the placebo group.

Blood samples for the lipid profile must be obtained under fasting conditions (ie, after the participant has fasted for approximately 10 hours). For the purposes of this study, fasting will be defined as nothing by mouth except water and any essential medications. If a participant is not fasting, the Investigator should reschedule the visit as soon as possible. LDL-C level will be calculated using the Friedewald equation unless $TG \ge 400 \text{ mg/dL}$ or LDL-C $\le 50 \text{ mg/dL}$; in both cases, LDL-C level will be measured directly by preparative ultracentrifugation, also referred to as beta quantification.⁷ In addition, for all patients, LDL-C will be measured by preparative ultracentrifugation, also referred to as beta quantification, at baseline (Visit 2) and at the end of the 8-week Treatment Period (Visit 4).

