9.2.5 Sample Size Determination

A sample size of at least 108 evaluable participants (ie, 36 participants per treatment group) will provide >90% power to detect a 30% difference in LDL-C reduction at Day 56 (SD of 15%) for each of the obicetrapib groups compared to the placebo group at a 2-sided significance level of 0.025.

The sample size for this study was determined in order to provide sufficient power for the analyses of the primary efficacy endpoint described in Section 7. Therefore, assuming an approximately 5% dropout rate, enrollment of approximately 114 participants (ie, 38 participants per treatment group) is planned for this study. This sample size will also contribute sufficient participant exposure and safety data.

Participants will be stratified according to their Screening Visit (Visit 1) LDL-C levels (≥100 or <100 mg/dL).

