APPENDIX A: SCHEDULE OF PROCEDURES

	Screening ^{a,b}	Treatment Period		Safety Follow-Up PK			Early	
Visit	1	2	3	4	5	6	7	Termination
Week	Up to -2	0	4	8	12	16	23	Visit
Day (± Visit Window)	-14 to -1	1	28 (±2)	56 (±2)	84 (±2)	112 (±2)	161 (±2)	Unscheduled
Informed consent ^c	X							
Inclusion/exclusion criteria	X	X^d						
Demographic information	X							
Medical/surgical history	X							
Prior/concomitant medications	X	X	X	X	X			X
Weight and height ^e	X							
Physical examination	X			X				
Vital signs ^f	X	X	X	X	X			X
12-lead ECG ^g	X							
Urine pregnancy test ^h	X						X	X
FSH test ⁱ	X							
Fasting (approximately 10 hours)	V	v	V	v	v	V	v	V
chemistry and hematology	X	X	X	X	X	X	X	X
Fasting (approximately 10 hours) lipid profile ^k	X	X	X	X				X
PK sample ¹	Λ	X	X	X	X ^m	X	X	X
Randomization		X	Λ	Λ	Λ	Λ	Λ	Λ
		X	X					
Dispense study drug				37				
Study drug administration ⁿ		X	X	X				
Study drug compliance	37	37	X	X				37
Register visit in IRT	X	X	X	X	77	***	37	X
Adverse events	1 1	X	X	X	X	X	X	X

Note: When several assessments are required at the same visit, samples for clinical laboratory assessments should be collected after completing other assessments, such as physical examinations, vital signs, and 12-lead ECGs.

Note: In cases of COVID-19 limitations, it is the Investigator's responsibility to assure the safety of participants, including phone or video contact to assess the participant's well-being including any adverse event, collection of study samples and clinical data as best as possible, and direct shipment of study drug to participant, if necessary. Where available and appropriate, home health care may be considered to facilitate monitoring of safety and study continuity. Documentation of these cases and the site's management of participants should be recorded in the Investigator study files. In the absence of a COVID-19 impact, it is expected that Investigators and participants follow the protocol requirements as set forth.

a. If laboratory abnormalities during screening are considered by the Investigator to be transient, then the laboratory tests may be repeated once during screening. The Investigator's rationale for retesting should be documented. If the retest result is no longer exclusionary, the participant may be randomized.

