#### 3.1.3 Definition of Baseline

Unless otherwise stated, Baseline will be defined as the last measurement prior to the first dose of study drug.

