#### 3.4.2 Secondary Efficacy Endpoints

Similar MMRM models as described for the primary efficacy analyses will be used to analyze the secondary efficacy endpoints. No adjustment will be made for multiplicity in testing the secondary efficacy endpoints. Nominal p-values will be provided when applicable. The following endpoints will be examined:

- Percent change from Day 1 to Day 56 in ApoB for each obicetrapib group compared to the placebo group;
- Percent change from Day 1 to Day 56 in non-HDL-C for each obicetrapib group compared to the placebo group; and
- Percent change from Day 1 to Day 56 in HDL-C for each obicetrapib group compared to the placebo group.

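### The secondary and other lipid models use one of two available pre-treatment values; adding each analyte's own Visit 1 value should narrow the Day 56 intervals by roughly 1-10%

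*Protocol*

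**What the plan says.** Protocol section 7 and SAP 2.3.2 name three key secondary endpoints: percent change to Day 56 in ApoB, non-HDL-C and HDL-C, each dose against placebo. The HDL-C one reads "Percent change from Day 1 to Day 56 in HDL-C for each obicetrapib group compared to the placebo group".

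The schedule in protocol Appendix A (SAP Table 1) has a row "Fasting (approximately 10 hours) lipid profile" marked at Screening (Visit 1, Day -14 to -1), Day 1 (Visit 2), Day 28, Day 56 and Early Termination. SAP Appendix B lists ApoB, HDL-C and non-HDL-C in that panel and does not restrict them to particular visits.

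SAP 3.1.3 states that "Baseline will be defined as the last measurement prior to the first dose" of study drug, which is normally the Day 1 value. The primary model (SAP 3.4.1) has treatment, visit, treatment-by-visit and Baseline as a continuous covariate. For the secondary endpoints, SAP 3.4.2 says "Similar MMRM models as described for the primary efficacy analyses will be used", and SAP 3.4.3 says the same for ApoE, HDL-ApoE, triglycerides and VLDL-C. Neither document uses the Visit 1 value of any of these analytes in an analysis. Visit 1 LDL-C serves eligibility and stratification only.

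**The concern.** A single blood draw carries visit-to-visit and assay noise. Here one draw is both the denominator of the percent change and the only baseline covariate. Having Day 1 in the model removes part of that noise. A second draw of the same analyte, taken 1 to 14 days earlier on a stable statin dose, would be expected to remove more.

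Visit 1 precedes randomization, so treatment cannot affect it and adjusting for it does not bias the contrast. The LDL-C stratum is no substitute: SAP 3.4.1 leaves it out of the model, and LDL-C cannot be assumed to stand in for HDL-C.

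What is at stake is precision. The sample size was set on LDL-C alone, and the key secondary endpoints are reported with nominal p-values, so interval width is much of what they convey.

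**Working it through.** **The plan's own figure.** Protocol 9.2.5 says that "at least 108 evaluable participants (ie, 36 participants per treatment group") "will provide >90% power" for a "30% difference in LDL-C reduction at Day 56 (SD of 15"%), "at a 2-sided significance level of 0.025".
- Standard error of a difference: 15 × √(2/36) = 3.54.
- 30/3.54 = 8.49, and 8.49 − 2.24 = 6.24, so power exceeds 0.9999. The claim is true.
- Dropout: 36/0.95 = 37.9, giving 38 per group; 108/0.95 = 113.7, giving 114. Both reproduce.

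**Reference interval.** No SD is given for ApoB, non-HDL-C or HDL-C. Borrowing the LDL-C SD of 15 as an assumption, the unadjusted 95% half-width with the Day 1 covariate only is 1.983 × 3.54 = 7.01 points.

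**Adding Visit 1, closed form.** Assume equal correlation r between any two visits. Residual variance with two pre-treatment values relative to one is (1 + 2r)/(1 + r)². The width ratio is its square root times about 1.005, the price of the extra covariate.

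**Check by simulation.** 36 per group, log-normal analyte, percent change at Days 28 and 56, unstructured two-visit model as in the SAP, 1,500 runs per setting. The last column is for no treatment effect.

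| r (assumed) | Variance ratio | Width ratio | Half-width | Simulated width ratio |
|---|---|---|---|---|
| 0.3 | 1.6/1.69 = 0.947 | 0.978 | 6.86 | 0.979 |
| 0.5 | 2.0/2.25 = 0.889 | 0.948 | 6.64 | 0.950 |
| 0.7 | 2.4/2.89 = 0.830 | 0.916 | 6.42 | 0.920 |
| 0.8 | 2.6/3.24 = 0.802 | 0.900 | 6.31 | 0.909 |
| 0.9 | 2.8/3.61 = 0.776 | 0.885 | 6.21 | 0.903 |

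Other settings of the same simulation:
- About a 30% fall: 0.953 to 0.905 for r = 0.5 to 0.9.
- About a doubling, as for an HDL-C-type rise: 0.954 to 0.909.
- Half the within-person noise drifting slowly (28-day half-life): 0.973 to 0.941.
- Visit 1 carrying nothing beyond Day 1: 1.005.

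Mean estimates and coverage were essentially unchanged by the added covariate. Break-even is a partial correlation of about 0.10 between Visit 1 and the Day 56 outcome given Day 1: √(1 − 0.10²) × 1.005 = 1.000.

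**Response heterogeneity.** The settings above let every participant respond alike. A second simulation (ANCOVA at Day 56, 36 per arm) varied the response. All its inputs are assumed: between-person SD 20-30%, within-person SD 6-10%, response heterogeneity SD 0-20%. The variance of the Day 56 contrast fell by about 5-19% for ApoB and non-HDL-C (effect −25%) and 2-20% for HDL-C (effect +50% or +130%). In width:
- ApoB or non-HDL-C, one middle setting: contrast SD 3.16 to 2.91, so 1 − 2.91/3.16 = 7.9%.
- HDL-C at +130%: 7.32 to 6.90, so 1 − 6.90/7.32 = 5.7%.
- Within-person SD 6% with heterogeneity 20%: about 1%.

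**Entry selection.** Screening LDL-C above 70 mg/dL restricts the Visit 1 range of correlated analytes. With an assumed correlation of 0.9 and a cut at the mean or 0.5 SD below it, gains of 4.5-6.3% in width fell to 2.9-5.2%. They shrank but did not vanish.

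**In participants.** A variance reduction f is worth 36/(1 − f) per arm: 36.7 at 2% and 45 at 20%, so roughly 1 to 9 extra evaluable participants per arm.

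**The case against.** The strongest reply is that nothing is broken. Percent change from Day 1 with the Day 1 value as covariate is coherent, pre-specified and valid, and the same covariate set is used throughout. The secondary endpoints have no multiplicity control and no success rule, and no comparison between the two active doses is planned. On the effects assumed above, ApoB moves from 25/3.16 = 7.9 standard errors to 25/2.91 = 8.6, and HDL-C from 130/7.32 = 17.8 to 130/6.90 = 18.8. No conclusion turns on that. All of this stands, and it is why the point is optional. It does not remove the gain in precision.

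A reader might also infer that the narrowing is free and certain. The documents do not support that. They give no between-visit correlation or SD for these analytes, and the covariate uses a degree of freedom. Narrowing occurred in about 66-99.9% of simulated trials, depending on the setting, and in only 14-17% in the limiting case where Visit 1 adds nothing.

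A bare instruction to add the Visit 1 value would be incomplete. The mITT definition requires only an LDL-C Baseline, and SAP 3.1.5 imputes nothing for secondary endpoints, so a participant without the new covariate would leave the model. If Day 1 is missing, Baseline falls back to Visit 1 and the two covariates coincide. Protocol 4.3 and 4.4 allow retests and rescreening, so the Visit 1 value needs a definition.

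**Conclusion.** The point holds as an optional efficiency gain of minor importance. Two pre-treatment values of each analyte are collected and one is used. Adding the other is expected to narrow the Day 56 intervals by roughly 1-10% in width, or about 2-20% in variance. The gain is smallest when response heterogeneity is large.

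The size rests on assumed within-person, between-person and response variability; only the direction follows from the design, and it requires some visit-to-visit or assay noise. It would be wrong to infer that the planned contrasts are biased or that the secondary conclusions are at risk. The same step is open for primary LDL-C, but power there is already above 0.9999.

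**What to change.** Before the unblinding described in SAP 4.2, amend SAP 3.4.2 and 3.4.3, and protocol 9.2.1.2, to add the analyte's own Visit 1 value as a second continuous covariate beside Baseline in each secondary and other lipid model. Leave the percent-change definition as it is. State also:
- The Visit 1 value is the one from the screening that led to randomization, and the last one if retested.
- A missing Visit 1 value is filled by a rule blind to treatment, for example prediction from the Day 1 value or the overall mean, so that nobody leaves the model.
- A like rule applies when Day 1 is missing and Baseline falls back to Visit 1.

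The cost is a few lines of SAP text and one degree of freedom. No new sample or visit is needed.
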